Coaching calls: Coaching calls with the implementation research team on use of quality improvement tools (workplan development, audit and feedback methods, plan do study act [PDSA] cycles, process mapping, and workflow analysis) and data collection methods. Coaching will also support partnering with local community organizations to engage priority populations in testing. Calls will be monthly with and biweekly email communications at a minimum, with additional coaching based on CHC's needs.

Training: Training topics include workflow analysis methods, COVID epidemiology, testing technology, local/state testing policies, disparities, stigma and discrimination, and cultural competency. Trainings will be delivered in meetings with the study implementation team and via listserv which includes participating CHCs.

b. Drugs to be used (dose, method, schedule of administration, dose modifications, toxicities), include Toxicity Grading Scale (if applicable)

None

c. Devices to be used

Testing will be done with normal CHC testing workflows with the addition of testing capacity made available by the Broad Institute for RADx-UP recipients, and rapid antigen testing made available from the state, the Abbott BinaxNOW and Acon Laboratories FlowFlex antigen tests. The Broad Institute is making available a self-administered anterior nares PCR testing option for RADx-UP awardees.

d. **Procedures/surgical interventions, etc.**

None

e. **Data to be collected and when the data is to be collected**

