The following data elements will be collected at each CHC as part of routine care to supplement EHR data. At MGH CHCs this is collected using an online REDCap survey or paper version of the REDCap survey. The paper REDCap survey will be entered into REDCap by a member of the research team. Federally qualified CHCs will use data collection methods (paper survey, online survey, phone) consistent with their usual care workflows for patient data collection aiming to improve clinical processes and understand the reach of services offered:

- Do you speak a language other than English at home? What languages?
- What is the highest level of education you have achieved outside or in the US?
- Including you, how many people live in your household?
- Are you currently living in transitional housing, staying in a shelter, or experiencing homelessness?

- Have you, or has anyone in your household experienced a loss of employment income since the start of the COVID-19 pandemic (March 2020)?
- Are you considered an essential worker? An essential worker is someone who was required to go to work even when stay at home orders were in place.
- Do you have a disability that interferes with your ability to carry out daily activities? Examples of daily activities include walking, climbing stairs, shopping, balancing a checkbook, bathing or dressing.
- It is easy to get tested for COVID-19.
- How likely are you to get an approved COVID-19 vaccine when it becomes available.
- Why would you get a COVID-19 vaccine?
- Why would you NOT get a COVID-19 vaccine?

Specific data to be collected through the individualized implementation support meetings with CHC staff will include details of their expanded testing strategy, populations reached, successes, challenges, how they are addressing equity and ways the implementation research team can support their site.

The data collected for the MGH sub study will not be shared with data coordinating center at Dana Farber.

b. Study endpoints

The primary outcome will be total number of daily and weekly tests. Secondary outcomes will include time to return of results, number of positive tests, completion of contact tracing, number of hospitalizations, intensive care admissions, and deaths. We will examine outcomes related to key socio-demographic and clinical covariates.

VII. RISKS AND DISCOMFORTS (Stratify by common and uncommon)

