### ***Statistical power and sample size***

For the overall primary outcome of number of COVID-19 tests, we used an interrupted time series design, comparing the aggregated number of tests across the 6 RADx-MA before and after implementation. We conducted a simulation study to estimate power to detect a 3.5% acceleration in weekly testing at an  $\alpha = 0.05$  significance threshold. Population parameters were determined based on a preliminary analysis of a testing time series from 4 CHCs with available testing data between May 1 and July 11, 2000 (when testing was more widely available in Massachusetts). We observed an average of 212 tests per day, a flat time-trend, and no significant autocorrelation after adjusting for seasonality related to the day of the week. Further, we assumed 518 days in the time series with an equal number of days pre- to post-implementation. Based on these assumptions we estimated greater than 90% power to detect 3.5% weekly acceleration in testing.

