### *Interrupted Time Series*

We characterized the implementation timeline of the planned testing acceleration strategies including funding notification and the start date of implementation activities. For the implementation activities start date, we considered that the CHCs made decisions about staffing and activities at the point of funding notification with the understanding that significant resources for RADx-MA were coming. They were then asked to start implementation activities with practice facilitation support on December 1, 2020. We considered both timepoints in the analyses and interpretation. We aggregated daily testing across the six CHCs and compared post-implementation testing trend with pre-implementation testing trend. Tests per week were modeled using segmented generalized linear model with number of weeks since start of pre-implementation period, indicator for pre- vs. post-implementation date, number of weeks post-implementation, weekly number of new state-wide covid cases, interactions of new covid cases with post-implementation week, and season of year to control for seasonality. Weekly number of new covid cases was included on the log-scale, centered at the number of cases on the implementation week, and divided by 10 to aid in interpretation. The coefficients of interest were for (a) the post-implementation week and (b) the interaction of post-implementation covid cases and post-implementation week. The former estimates the change in covid testing trend post-implementation relative to pre-implementation holding new covid cases at the implementation week level. The latter estimates the percentage change in covid testing trend post-implementation relative to pre-implementation for a 10% increase in new covid cases. We used heteroscedastic and autocorrelation consistent standard errors implemented using the Sandwich package in R. We consider  $\alpha=0.05$  as the threshold for statistical significance.

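### With no external testing series in the model, a statewide change in testing trend that starts at the interruption cannot be told apart from coefficient (a)

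*SAP*

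**What the plan says.** The SAP (Interrupted Time Series) models weekly tests summed over six CHCs. The time terms are week, a pre/post indicator and weeks since implementation. The remaining terms are "weekly number of new state-wide covid cases, interactions of new covid cases with post-implementation week, and season of year to control for seasonality". Two coefficients are of interest: (a), the change in testing trend with cases held at their implementation-week level, and (b), the case interaction. The level indicator is not one of them. Activities began on 1 December 2020; the funding notification date is also considered.

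Protocol section III.a says a controlled series was planned but no suitable control could be found. The same section still describes matched CHCs as a second group, and section IX.b still lists six control CHCs. Aim 1 (section II) uses the controlled version of the design to evaluate the impact of the outreach and capacity building.

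The documents also show influences on testing that are neither cases nor season. Section V.c lists "rapid antigen testing made available from the state". The survey in section VI.a asks "How likely are you to get an approved COVID-19 vaccine when it becomes available", while vaccine status, type and date are also collected, which suggests that vaccines arrived during the study.

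**The concern.** Test supply, the opening or closing of other sites and vaccine availability can change how many tests are done at a given number of cases. Adjusting for cases does not remove such changes. If they alter the testing trend across the state after the interruption, (a) contains the programme effect plus that drift. A statewide rise could look like a gain, and a statewide fall could hide one. With no comparison series, nothing in the model can show which has happened. Moving the interruption to the funding notification date does not help, because that supplies no outside comparison either.

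**Working it through.** **The plan's own figure.** Inputs from the SAP power section: "We observed an average of 212 tests per day, a flat time-trend, and no significant autocorrelation"; "518 days in the time series with an equal number of days pre- to post-implementation"; significance level 0.05 (two-sided assumed). Then 212 × 7 = 1,484 tests per week and 518 / 7 = 74 weeks, 37 on each side. A 3.5% weekly acceleration is ln(1.035) = 0.0344 per week. A Poisson log-linear model with time terms only gives a slope-change standard error of 0.0005, so power is about 100%. This agrees with "we estimated greater than 90% power to detect 3.5% weekly acceleration in testing", and power stays above 90% up to a weekly residual coefficient of variation (CV) of about 0.4 (97.7% at 0.4, 88.5% at 0.5). So the power claim reproduces. It concerns precision and says nothing about what (a) measures.

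**Where a statewide shift goes.** The link is not stated; a log link is assumed. With W the weeks since implementation (0 before), P the post indicator and C the centred log cases:

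log E(tests) = b0 + b1·week + b2·P + b3·W + b4·C + b5·C·W + season

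Here (a) = b3 and (b) = b5. Let the programme's true slope effect be d. Let statewide testing at fixed cases drift by s·W, and let the CHCs follow it with elasticity e. The drift is an exact multiple of the W column, so (a) = d + e·s. No diagnostic or longer series can separate the two parts.

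Hypothetical shifts with d = 0 and e = 1, projected onto this design by least squares:

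| Statewide shift | Effect on (a), per week |
|---|---|
| Ramp of 1% per week from the interruption | +0.0100 |
| +20% step at the interruption | 0 (level indicator takes +0.200) |
| Winter-season shift | 0 |
| Shift proportional to cases in all weeks | 0 |
| Case response growing with W | 0 (all in (b)) |
| Ramp of 1% per week starting 12 weeks later | +0.0026 to +0.0091 |
| Lasting −20% step at week 18 | −0.0051 to −0.0097 |
| Temporary +20% in weeks 0–11 | −0.0004 to −0.0041 |

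The first five rows are algebraic and do not depend on the case curve. The ranges come from three assumed case curves and are not bounds.

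**Consequence for the test of (a).** Illustration with assumed values: d = 0, s = 1% per week, CHC residual CV 10%, statewide series with 10% variation of its own that the CHCs share in proportion to e, independent errors, two of the case curves.
- e = 1: mean (a) is about 0.010, and the null is rejected in 16% to 33% of runs.
- e = 0.5: mean (a) is about 0.005, with rejection in 9% to 17%.
- Log statewide tests added with a free coefficient: mean (a) is about 0.000, with rejection in 4.6% to 5.5%.

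**Limits of each adjustment.** The same model fitted to the external series gives (a) = s. The CHC-minus-external difference, or an offset, is therefore d + (e − 1)s. With d = 0 and s = −2% per week:
- e = 0.5: unadjusted 0.5 × (−2) = −1.0%; difference (−0.5) × (−2) = +1.0%.
- e = 0: unadjusted 0; difference (−1) × (−2) = +2.0%.

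A free coefficient has a different weakness. At 1% drift and e = 1, it leaves (a) at about 0.010 if the CHCs share none of the external week-to-week variation, about 0.005 if they share half, and about 0.000 if they share all of it.

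**The case against.** The strongest reply is that this is the known limit of any single-group interrupted time series. The sponsor planned a control, looked for one and reported that none was suitable. The SAP words (a) as a change in trend at fixed cases, not as a programme effect. The model already separates steps, season and case-driven changes, and real shocks such as site openings are more likely to be steps, temporary or delayed than ramps beginning exactly at the interruption. Section II also says the partnership draws on the State's testing resources, and section V.c lists state-supplied antigen tests among the devices used. State supply is thus partly a channel of the intervention, and netting it out changes the quantity estimated.

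Most of this stands, and it is why the remedy is a sensitivity analysis. It does not remove the confounding of a trend change that starts at the interruption, and Aim 1 does ask about impact.

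A reader might go further and infer that every statewide shift passes one-for-one into (a), or that the programme will be credited with gains it did not make. The table rules out the first. The second needs a direction of drift, which the documents do not give. Nor can the bias be sized as a share of the 3.5% target: a simulation that puts s in only returns s. An offset may seem the obvious cure, but it can create an effect when elasticity is below 1.

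**Conclusion.** The point holds in a limited form. A case-independent change in statewide testing trend from the interruption onward is inseparable from (a), entering as e·s. Other shifts either have their own terms or reach (a) only in part, sometimes with reversed sign. No bias is shown to have occurred, and its size and direction cannot be computed from the documents. The conclusion rests on the log link; the illustrative sizes also rest on a 37/37-week split and on assumed case curves and noise. Some SAP text ahead of the power section was not available for this check. The gap limits how (a) may be interpreted; it does not invalidate the model or the power figure.

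**What to change.** 1. As a labelled sensitivity analysis, fit the identical segmented model to an external weekly testing series: statewide tests less the six CHCs, if published, or the non-participating CHCs in DRVS. Section IX.b says DRVS holds testing data on all 52 Massachusetts CHCs.
2. Report its (a) and (b) beside the CHC estimates, with the difference and its interval. Call the series a benchmark, not a matched control.
3. State that the difference, or an offset, assumes elasticity 1. Show alongside it a version with a free coefficient on log external tests, noting that this removes drift only where the two series share week-to-week variation.
4. Note that state supply is partly a programme resource, so the difference may net out some of the programme.
5. If the benchmark shows a similar trend change, or no series can be obtained, describe (a) as a post-implementation trend change and not as a programme effect.

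The cost is one more weekly series and a few additional fits. The benchmark will be imperfectly comparable, and the interval for the difference will be wider. Availability is an assumption: the documents give no statewide test counts, and the planned DRVS extract covers only the partner and control CHCs.

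### The weekly model has no holiday or open-days term, although Thanksgiving, Christmas and New Year fall in high-leverage weeks beside the December 1, 2020 interruption

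*SAP*

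**What the plan says.** The SAP (Interrupted Time Series) sums tests over six health centers by week and fits a segmented generalized linear model. The time terms are "number of weeks since start of pre-implementation period, indicator for pre- vs. post-implementation date, number of weeks post-implementation". The remaining terms are weekly state-wide new cases on the log scale, their interaction with the post-period week count, and "season of year to control for seasonality". Two coefficients are of interest. Coefficient (a) is the post-implementation week term: "The former estimates the change in covid testing trend post-implementation relative to pre-implementation", with cases held at their implementation-week level. Coefficient (b) is the interaction of cases with post-implementation week.

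The centers were asked to "start implementation activities with practice facilitation support on December 1, 2020". Funding notification is a second candidate interruption, and its date is not given: "We considered both timepoints in the analyses and interpretation".

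The SAP sections available for review do not mention holidays or days open. The power section reports "no significant autocorrelation after adjusting for seasonality related to the day of the week", so day of the week was treated as a source of variation in daily counts.

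**The concern.** Summing to weeks removes day-of-week variation but not differences between weeks in the number of working days. A season term takes one value for about 13 weeks, so it cannot represent a change confined to one of them.

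The position of the holidays makes this matter. A low count in the last pre-implementation week pulls the pre-slope down. Low counts early in the post-period pull the post-slope up. Coefficient (a) is the difference between the two slopes, so dips in all three weeks add together instead of cancelling. If they occurred, part of a positive (a) would be calendar and not programme. An unusual rise in those weeks would distort (a) the other way.

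**Working it through.** **Inputs from the documents.** Interruption on December 1, 2020; weekly model terms as listed above; heteroscedasticity- and autocorrelation-consistent (HAC) standard errors; α = 0.05; planning effect 3.5% per week. From the power section: 212 tests per day, so 212 × 7 = 1,484 per week, and 518 days split equally, so 518 / 7 = 74 weeks, or 37 + 37. That window is a power assumption. The SAP does not give the actual analysis window.

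**Inputs assumed.** Size of the dip (1/7, about 14%, for one closed day in seven; 20%; 30%), the case curve, the definition of season, and week-to-week CV. The documents give none of these.

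**Plan's own figure.** Simulating a 3.5% weekly acceleration with these inputs gives 100% power in the daily layout. In the weekly 37 + 37 layout it gives 100% at CV 3% and 18%, 99.8% at CV 37% and 95% at CV 58%. The stated power above 90% reproduces.

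**Calendar.** December 1, 2020 is a Tuesday. With Tuesday-to-Monday weeks, November 26 lies in the last pre-week, December 25 in post-week 4 and January 1 in post-week 5. Sunday-to-Saturday and Monday-to-Sunday weeks give the same placement.

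**Plain segmented model, by hand.** With n = 37 weeks per segment, Sxx = n(n² − 1)/12 = 37 × 1,368 / 12 = 4,218, and the mid-point is week 19.
- Thanksgiving is pre-week 37, which is 37 − 19 = +18 from the mid-point. A dip d changes the pre-slope by −18d/4,218.
- Christmas and New Year are post-weeks 4 and 5, at −15 and −14. They change the post-slope by +29d/4,218.
- The change in (a) is about (18 + 29)d/4,218 = 47d/4,218.

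This gives 0.159%, 0.223% and 0.334% per week for d = 1/7, 0.20 and 0.30. Noise-free Poisson log-link fits give +0.16, +0.23 and +0.34%.

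**Adding the SAP's other terms** (no true effect, 37 + 37 weeks, one assumed winter-peak case curve):

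| Dip in each week | Meteorological seasons, no cases | Meteorological seasons and cases | Astronomical seasons and cases |
|---|---|---|---|
| 1/7 | +0.12 | +0.42 | +0.74 |
| 20% | +0.17 | +0.59 | +1.04 |
| 30% | +0.25 | +0.90 | +1.58 |

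Other assumed case curves give +0.42 to +1.28% for 20% dips and +0.64 to +1.94% for 30% dips.

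**Sensitivity to layout.**
- Over 143 weeks the spurious (a) falls to +0.07 to +0.19% per week.
- With the interruption 4 to 12 weeks earlier (20% dips, no case terms) it is −0.004 to +0.16%. With case terms, 4 to 10 weeks earlier, it is +0.02 to +0.28%.
- A 20 + 20 window with season and case terms is unstable (−0.75 to +4.07%).

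**Sensitivity to sign** (37 + 37).
- A 20% rise in all three weeks gives −0.17% with season terms and −0.56% with the case curve added.
- A Thanksgiving rise followed by dips gives −0.01% with season terms.

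**False positives under HAC errors** (4 lags, 600 runs per setting, season and case terms, no true effect). Share of runs with a significant positive (a):

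| Weekly CV | 20% dips, no holiday term | No dips, or dips with the term |
|---|---|---|
| 5% | 30% | about 10% |
| 10% | 22% | 8 to 9% |
| 18% | 17% | 10 to 12% |

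The right-hand column already exceeds the 2.5% expected in one direction. That is a separate small-sample property of these standard errors. Only the difference between the columns belongs to the holidays.

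**Effect of the remedy.** One common indicator returns (a) to 0.00 when the dips are equal. With 20% rises at Thanksgiving and Christmas and a 20% dip at New Year, two assumed case curves give −0.26 and −0.45% without a term, and −0.16 and −0.27% still with one common indicator. One indicator per week returns (a) to 0.00 whatever the signs, because it is equivalent to omitting the three weeks.

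**The case against.** The strongest reply is that the dips are not in evidence. No section gives holiday counts, closures or opening days. A weekday pattern at four centers between May and July does not establish the net volume of a holiday week, which may include demand before travel or gatherings. That stands: the direction is conditional.

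The larger figures also depend on case curves, season definitions and a window that the documents do not supply. If reported cases fell by 20% in the same weeks, two fits drop from +0.52 to +0.44% and from +0.87 to +0.62%. This limits the size but does not remove the effect. Adding 14% dips in ten other holiday weeks did not cancel it either: two fits gave +0.47 and +0.49%, against +0.46 and +0.55% without them.

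The SAP considers two interruption dates. If notification came earlier than December 1, Thanksgiving moves into the post-period and the tilt is generally smaller. Comparing the dates is then a partial internal check, but the two estimates could also differ through the calendar alone.

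A reader might infer that the bias must favour the programme, or that it undermines the Aim 1 conclusion. The documents support neither. The sign reverses if those weeks surged, and the SAP names two coefficients of interest and no rule by which (a) alone decides the aim.

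**Conclusion.** The omission is real and sits beside the interruption, where it matters most for (a). Its direction and size cannot be settled from the documents. Under assumed dips of 14% to 30%, 37 + 37 weeks and no true effect, (a) is inflated by about 0.16 to 0.34% per week in a plain model, and by roughly 0.4 to 1.9% with season terms and assumed case curves.

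In that window the tilt stays below 3.5% per week, so it could not by itself produce the planned effect. The risk is to the reading of a small significant (a), mainly when weekly noise is low; at CV 18% the excess in false positives is about 5 to 7 percentage points. This is a low-cost improvement to the specification. It does not show that the result is wrong.

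**What to change.** Add to the weekly model an indicator for the weeks containing Thanksgiving, Christmas and New Year's Day. Preferably use one indicator for each of the three weeks, so that unequal or opposite effects are also handled. The number of testing days open each week, as a covariate or offset, is an alternative where the centers can supply it. Apply the same term at both interruption dates, and report (a) with and without it at each.

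The indicators need no new data, since the holiday dates are public. The cost is one degree of freedom for a common indicator or three for separate ones. The SAP describes the modelling as already done, so a short reanalysis is also needed. If the holidays had no effect, only the degrees of freedom are lost.
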